- between 2.8 and 3.8 cm H₂O/l/s, inclusive, have indeterminate EFL. Some breaths were calculated to be flow limited.
- greater than 3.8 cm H₂O/l/s have EFL.

For purposes of this trial, participants who have indeterminate EFL or EFL (i.e., $\Delta\bar{X}_{rs}$ value is greater than or equal to 2.8 cm H₂O/l/s) will continue to titration.

This technology has been evaluated in numerous clinical studies for both the detection, reduction and abolishment of expiratory flow limitation in patients with COPD. In 1956, Dubios et al., demonstrated the FOT method to be applicable to the measurement of airway resistance in patients, evaluation of therapeutic procedures designed to relieve airway obstruction, separation of airway resistance from tissue resistance, and study of the multiple factors that may affect airway resistance.¹ And in additional work 2006, Dellaca et al., suggested the forced oscillation technique may be useful in chronic obstructive pulmonary disease patients using nasal pressure support by identifying continuous positive

Determination of the Prevalence and Severity of Expiratory Flow Limitation in Chronic Obstructive Pulmonary Disease Patients

airway pressure levels that support breathing without increasing lung volume, which in turn increase the work of breathing and reduce muscle effectiveness and efficiency.⁶

The Vector project has incorporated this method as a new feature into the Philips BiPAP Ventilator (Murrysville, PA) overall platform (K121623). The device has been designed to produce a 5 Hz sine wave with peak-to-peak amplitude of approximately 2 cmH₂O superimposed upon the pressure and flow generated by the device. The resultant feedback waveform is then filtered and analyzed to measure reactance (delta X_{rs}) and thus determine if EFL is present. Subsequently, the EPAP (and concurrently and proportionally the IPAP) is increased until the EFL is essentially abolished (falls below the predetermined EFL threshold). Since this reactance is analyzed continuously (breath by breath) during both inspiration and expiration, it is relatively immune to external factors such as modest leaks or coughing / swallowing.

Description of the Intervention Studied

Study Device Descriptions:

1. Vector Device

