The Vector ventilator is intended to provide non-invasive ventilatory support to treat adult patients with Respiratory Insufficiency with the primary cause being COPD. It is intended to be used within the home, institution/hospital, and diagnostic laboratory environments. This device is not intended for life support. It can be used to screen for the presence, and abolition, of Expiratory Flow Limitation.

The Vector ventilation method auto-titrates PEEP or EPAP on a breath by breath basis. Vector is a new noninvasive method to continuously detect EFL during spontaneous breathing and minimizing it using EPAP.

The device has been designed to produce a 5 Hz sine wave with peak to peak amplitude of approximately 2 cmH₂O superimposed upon the pressure and flow generated by the device. The resultant feedback waveform is then filtered and analyzed to detect the change of a reactance (delta X_{rs}). Subsequently the EPAP (and concurrently and proportionally the IPAP) is increased until the EFL is essentially abolished (falls below the predetermined EFL threshold). Since this reactance is analyzed continuously (breath by breath) during both inspiration and expiration, it is relatively immune to external factors such as modest leaks or coughing / swallowing. Given that forced oscillation technique can be easily applied during noninvasive nasal ventilatory support, it could be used during routine noninvasive ventilation.

This Vector screening mode is an automated five-minute screening test that can be done in a clinical environment under supervision to determine if EFL is present and its level of severity.

Determination of the Prevalence and Severity of Expiratory Flow Limitation in Chronic Obstructive Pulmonary Disease Patients

The screening test will have built-in logic that determines the test's validity during the screening as well as the conclusion of the test. The screening test will be at a relatively fixed pressure (typically between 3-4 cmH₂O) that will remain constant throughout the session. The screening session results, which will consist of near real-time pulmonary mechanic information, will be kept on a display until the next session is enabled.

The Vector Ventilator is not currently approved by the FDA. It is considered an investigational device.

2. Resmon Pro Device

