The Resmon Pro (St. Paul, MN) also uses the forced oscillation technique (FOT) which is a noninvasive method to measure the mechanical properties of the lung and airways during tidal breathing. In addition to measuring total impedance (resistance and reactance), the Resmon Pro can measure expiratory flow limitation which is a key index of respiratory obstruction. Restech has developed patented technology to determine the breath-by-breath presence and severity of expiratory flow limitation (EFL) during quiet breathing. Using the Resmon Pro, a physician can detect the presence, severity and reversibility of EFL, and evaluate the degree of airflow obstruction and shortness-of-breath experienced by the patient.

The Resmon PRO FULL (K152585) is intended to measure respiratory system impedance using the Forced Oscillation Technique (FOT). Is intended for use with pediatric and adult patients 4 years of age or older. The device is designed to be used by pulmonologists, general practitioners, nurses, respiratory therapists, laboratory technologists, medical researchers and similarly trained personnel in hospitals, clinics, and private physician offices.

Resmon PRO FULL consists of a main unit which has been designed to be used stand-alone, without the need of any personal computer, and an adjustable holder with a clamp to fix such unit to a table/desk and to regulate its height and orientation to the patient during an FOT test.

II. Study Objectives and Purpose

Primary Objective

To gain insight and understanding on the prevalence and severity of expiratory flow limitation and how it relates to other physiological characteristics and endpoints in patients with COPD. For purposes of this trial, overall prevalence includes indeterminate EFL and EFL.

Secondary Objectives: To understand the correlation of the final EPAP with FEV1, final EPAP with screening delta Xrs value and the percent of participants with EFL per the Resmon Pro that have their EFL abolished during the Vector screening.

Primary Endpoint:

- Overall Prevalence of EFL, as defined as the percentage of participants exhibiting a Delta Xrs value greater than or equal to 2.8

Secondary Endpoint:

- Correlation of titrated Final EPAP to participants' FEV1
- Correlation of titrated Final EPAP to participants' screening Delta Xrs value
- Percent of participants with EFL per the Resmon Pro that have their EFL abolished during the Vector screening

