Exploratory Endpoints: – Correlation and relationship of participant's therapy settings to the following:

- Classification of COPD (Chronic Bronchitis or Emphysema)
- Airflow limitation severity in COPD via Global Initiative for Chronic Obstructive Lung Disease (GOLD) classification¹²
- Presence of indeterminate EFL and EFL in a seated position
- Presence of indeterminate EFL and EFL in a supine position
- Quality of Life via COPD Assessment Test (CAT)¹³ score
- Exacerbation History
- Healthcare Utilization
- Smoking History
- Oxygen therapy usage
- Documented PaCO₂
- Presence of Sleep Disordered Breathing and risk of obstructive sleep apnea (OSA) via STOP-BANG Questionnaire¹⁴
- Therapy Comfort assessment via Questionnaires

Determination of the Prevalence and Severity of Expiratory Flow Limitation in Chronic Obstructive Pulmonary Disease Patients

Device Related Exploratory Endpoints:

- Vector Device collected parameters: Delta Xrs value, % flow limited breaths, Total System Resistance mask leak values
- Comparison of Delta Rx calculation of the Resmon Pro at 5 Hz vs. Vector study ventilator
- Correlation between screening Delta Xrs (measurement in liters per second) at final EPAP in cmH₂O in supine position and any other variables from the analysis
- Therapy Comfort assessment via Questionnaires

Observational Endpoints/Learnings:

- Clinicians will be able to know when EFL is present or not present through the screening feature of the Vector device
- Understanding of how patients who present with varying degrees of EFL severity are being medically managed differently or similarly
- Percentage of patients that were successfully screened as not having EFL by the Vector device but determined to have flow limitation measured by Resmon Pro

III. Study Design:

This will be a cross-sectional, non-randomized epidemiology study designed to assess the prevalence and severity of expiratory flow limitation in a community COPD population. In the study we will also investigate how the presence of EFL may correlate to other physiological biomarker endpoints in the COPD patient.

Site COVID-19 safety procedures and documentation will be followed. Study devices and materials will either be single use or will be cleaned and disinfected per the Instructions for Use.

Schedule of Events:

Study Visit

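### The third secondary endpoint places EFL abolition in the constant-pressure Vector screening test, whereas Section IX analyses abolition by Vector therapy and does not carry over the Resmon-positive denominator

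*Combined protocol and SAP*

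**What the plan says.** All references are to the combined protocol and SAP.

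- **Section II, Secondary Objectives and Secondary Endpoint.** The quantity appears twice. The objective is to understand the "percent of participants with EFL per the Resmon Pro that have their EFL abolished during the Vector screening", and the endpoint list repeats it. The population is named: participants with EFL on the Resmon Pro. The event is abolition during Vector screening.
- **Section I, Vector Device.** "This Vector screening mode is an automated five-minute screening test" for the presence and severity of EFL. Its pressure, typically 3-4 cmH₂O, "will remain constant throughout the session". The same section says of the device: "It can be used to screen for the presence, and abolition, of Expiratory Flow Limitation".
- **Section III, Vector EFL Screening/Determination and EPAP Titration.** Participants found by Vector to have neither EFL nor indeterminate EFL stop before titration. Those at 2.8 or above are switched from screening mode to therapy mode. There, over about 20 minutes, the device raises EPAP until EFL is abolished or falls below a predetermined threshold.
- **Section IX, Secondary Analysis.** The percentage of participants with EFL abolition under Vector therapy is reported with a 95% binomial CI. The Resmon Pro is not mentioned.
- **Section II, Observational Endpoints.** A separate percentage covers patients "successfully screened as not having EFL by the Vector device but determined to have flow limitation measured by Resmon Pro".
- **Cut-offs.** Section I classes 2.8 to 3.8 as indeterminate and says that individuals "greater than 3.8 cm H₂O/l/s have EFL". Section II widens only the prevalence measure: "For purposes of this trial, overall prevalence includes indeterminate EFL and EFL".

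**The concern.** A test run at one constant pressure has no step that removes EFL; it finds EFL or it does not. Read literally, the endpoint counts people who had EFL on the Resmon Pro and did not have it at the Vector screening pressure. That number goes up when Vector detects fewer Resmon-positive participants, and it does not move with the success or failure of titration.

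An analyst working from Section II and one working from Section IX would therefore report different quantities under the same abolition label. Section XV says that the data may support regulatory clearance or publication. If the choice between the two is left until the data are in, a reader cannot tell whether it was made in advance.

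**Working it through.** The plan gives no expected rate, and Section IX says that no power analysis was done, so there is no stated figure to reproduce. The check is first textual, then illustrative.

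**1. The two definitions side by side**

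| | Section II | Section IX |
|---|---|---|
| Event | EFL abolished during screening | EFL abolished with therapy |
| Device mode | Screening, constant pressure | Therapy, EPAP rising |
| Population | EFL per the Resmon Pro | Participants, no condition stated |

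Section III makes the modes sequential and lets the Vector result, not the Resmon result, decide who is titrated. A Resmon-positive participant with a Vector value below 2.8 is never titrated, and no section says how that person counts towards abolition by therapy.

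**2. Illustration, cut-off of at least 2.8 on both devices**

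Assumed, not from the documents: one posture; 50 Resmon-positive; 10 of these Vector-negative; 50 − 10 = 40 titrated; 36 of the 40 successful. Intervals are exact (Clopper-Pearson) 95% limits, with x successes in n: lower = Beta quantile 0.025 (x, n − x + 1), upper = Beta quantile 0.975 (x + 1, n − x).

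| Reading | x/n | % | 95% CI |
|---|---|---|---|
| Literal Section II | 10/50 | 20 | 10-34 |
| Therapy, all Resmon-positive | 36/50 | 72 | 58-84 |
| Therapy, Resmon-positive and titrated | 36/40 | 90 | 76-97 |

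**3. The literal reading ignores titration**

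Keep the 10 Vector-negatives but let only 20 of 40 titrations succeed. The literal result is still 10/50 = 20%. Therapy success falls to 20/50 = 40% (26-55%) over all Resmon-positive and 20/40 = 50% (34-66%) over those titrated.

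**4. Effect of the cut-off**

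If EFL means above 3.8, a Resmon-positive participant who reads 2.8-3.8 on Vector no longer has EFL at screening, so is a literal success, and is nevertheless titrated. Suppose 6 of the 10 literal successes are of this kind. The literal figure stays at 10/50 = 20%, but 50 − 4 = 46 are titrated. At about 90% success (0.9 × 46 = 41.4, taken as 41), therapy gives 41/50 = 82% (69-91%) over all Resmon-positive and 41/46 = 89% (76-96%) over those titrated. The literal and therapy numerators can then share participants; in step 2 they cannot.

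**5. Overlap with the observational endpoint**

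Take screened as not having EFL to mean a Vector value below 2.8. At a cut-off of at least 2.8, the literal numerator and the observational endpoint count essentially the same people within a posture. At above 3.8 the overlap is partial: in step 4, 4 of the 10.

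**The case against.** The literal wording may be deliberate. The first two secondary endpoints refer to titrated Final EPAP and the third to Vector screening, so the authors distinguished the terms within one list, and the version 4.0 history entry records updates to objectives and endpoints. Screening does apply some pressure, so asking whether EFL seen on the Resmon Pro is absent at that pressure is coherent. This stands: the text does not settle which meaning was intended, and a reader who infers that titration must have been meant goes further than the documents allow. But the screening question is not the one that Section IX analyses, so the conflict remains.

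The opposite defence is that screening is shorthand for the whole Vector session. The device description and the intended use in Section V both link screening with abolition, and Section III puts screening and titration under one heading. This is also possible, but it leaves the Resmon-positive, never-titrated participants without stated handling.

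A reader might also infer that the plan has no denominator. It does: Section II names Resmon-positive participants, which on its face includes those never titrated. The gap is that Section IX does not repeat it, and a short methods paragraph can fairly be read together with the endpoint it serves.

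Finally, this is one descriptive percentage in an unpowered epidemiology study, and every count above is assumed. Both points limit the weight of the issue; neither reconciles the sections.

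**Conclusion.** The inconsistency holds and should be fixed. Section II and Section IX name different events for the same endpoint, and only Section II names the population. Followed literally, Section II measures absence of EFL at screening pressure and cannot show whether titration works.

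The 20%, 72% and 90% figures show that the readings can differ widely in the same participants. They are not forecasts, and they rest on the assumed counts, one posture, and a cut-off of at least 2.8 on both devices. Two stronger inferences fail for the same reason. Literal successes and titrated participants are complements only if EFL means at least 2.8 or if nobody reads 2.8-3.8 on Vector. Likewise, the endpoint nearly duplicates the observational discordance measure only at the lower cut-off. Section I's default for plain EFL is above 3.8, so neither can be taken for granted.

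The effect is confined to this secondary percentage. The primary prevalence endpoint and the sample size are not touched.

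**What to change.** Reconcile Sections II, III and IX so that one event and one denominator apply.

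- **If abolition by therapy is meant, as Section IX says:** in the Section II objective and endpoint, replace the reference to Vector screening with the Vector EPAP titration (therapy mode), and add the Resmon-positive denominator to Section IX. Report abolition over all Resmon-positive participants with its exact 95% CI. As a supplement, report it over those who started titration, and show the number never titrated.
- **If absence of EFL at screening pressure is meant:** name it so in Section II, and do not analyse it as abolition with Vector therapy in Section IX.
- **In either case:** confirm which Resmon posture defines the population, since that test is done seated and then supine or semi-recumbent while titration is supine or semi-recumbent only. Confirm whether EFL per the Resmon Pro means above 3.8 or at least 2.8, and apply the same cut-off to the numerator.

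The cost is a wording change, two confirmations and one extra percentage. Section VI already has Delta Xrs and EPAP recorded during screening and titration. The headline abolition figure will be lower if untitrated Resmon-positive participants are counted in the denominator; the documents give no basis for saying by how much.

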- Once the participant arrives, the study will be explained in full detail. If the participant agrees, he/she will be consented into the study and the participant will be given a copy of the informed consent.
- Once consent is obtained, and eligibility is confirmed the following study related procedures will be conducted:
- Demographics: gender, date of birth, ethnicity, race, level of education will be collected.
- Current Medications: all current medications will be collected.

Determination of the Prevalence and Severity of Expiratory Flow Limitation in Chronic Obstructive Pulmonary Disease Patients

- Medical History Assessment: information will be collected regarding historical spirometry data, COPD history and other relevant medical history including the diagnosis of Sleep disordered breathing and Oxygen therapy usage. Chest computerized tomography (CT) scans will be collected if they have been done within the past two years. A new CT scan will not be required.
- Physical examination with anthropometric data (weight, height, temperature) collected and vital signs to include heart rate (HR), blood pressure (BP), respiratory rate (RR), and oxygen saturation (SPO₂) maintained at least 88% on room air, and chest auscultation.
- Review of inclusion/exclusion to ensure participant is eligible to continue
- Administration of Study Questionnaires
- Mask Fitting: Participants will have up to two mask fittings in order to determine the best possible masks while using the Vector NIV device during the EFL screening and titration
- Spirometry testing will be performed for participants who have not had a test in the previous 6 months

Resmon Pro EFL Measurement

- Participants may be required to wear nose clips during the measurement
- Participants will also be required to hold their cheeks during the measurement to prevent any air leaks around their mouth.
- While seated, participants will be instructed to breathe normally into the device for at least 30 seconds or until at least 10 breaths were successfully accepted by the device
- Participants will be asked to repeat test while in the supine or semi-recumbent position.

Vector EFL Screening/Determination and EPAP Titration

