1. Any major non COPD uncontrolled disease or condition, such as congestive heart failure, malignancy, liver or renal insufficiency (that requires current evaluation for liver or renal transplantation or dialysis), amyotrophic lateral sclerosis, or severe stroke, or other condition as deemed appropriate by investigator as determined by review of medical history and / or participant reported medical history

Determination of the Prevalence and Severity of Expiratory Flow Limitation in Chronic Obstructive Pulmonary Disease Patients

2. Suffering from a COPD exacerbation at the time of data collection or in the 30 days prior to data collection
3. Self-reported Pregnancy
4. Employee or family member that is affiliated with Philips Respironics
5. History of bullous emphysema
6. History of pneumothorax
7. Evidence of acute sinusitis or otitis media
8. Hypotension
9. Participants at risk for aspiration of gastric contents
10. Epistaxis
11. Participants in respiratory failure
12. Inability to maintain a patent airway or adequately clear secretions

C. Withdrawal:

The term “discontinuation” refers to the participant’s premature withdrawal from the study prior to completing all procedures. Participants may be discontinued from the study for any of the following reasons:

- If in the investigator’s judgement, continuation in the study may prove harmful to the participant. Such a decision may be precipitated by adverse events, including fever, nausea, rash, changes in vital signs, or the development of a new medical condition. The investigator will be solely responsible for making medical/safety decisions regarding the participant’s continued participation in the study.
- Noncompliance;
- At the request of the participant.

The study team will document whether or not each participant completed the study. If, for any participant, study treatment or assessments were discontinued, the reason will be recorded.

The study goal is to have 100 participants successfully complete the study.

V. Treatment of Subjects:

A. Intended Use

Vector Device Intended Use

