The Vector ventilator is intended to provide non-invasive ventilatory support to treat adult patients with Obstructive Sleep Apnea (OSA), or Respiratory Insufficiency with primary cause being Chronic Obstructive Pulmonary Disease (COPD). This device is not intended for life support. It may be used to screen for the presence, and abolishment of Expiratory Flow Limitation. It is intended to be used within the home, institution/hospital, and diagnostic laboratory environments.

Determination of the Prevalence and Severity of Expiratory Flow Limitation in Chronic Obstructive Pulmonary Disease Patients

Contraindications:

- Existing respiratory failure
- Acute sinusitis, otitis media
- Hypotension
- At risk for aspiration of gastric contents
- Epistaxis, causing pulmonary aspiration of blood
- Inability to maintain a patent airway or adequately clear secretions

Resmon Pro Intended Use

The Resmon PRO FULL is intended for the measurement and collection of lung function parameters in humans. The system performs cooperation-independent measurements of respiratory system impedance using the Forced Oscillation Technique (FOT). The device is useful in the field of early diagnosis, in every-day-routine testing, for clinical trend observations as well as for epidemiologic studies. FOT is suitable for adult, geriatric and pediatric studies. The device is designed to be used by pulmonologists, general practitioners, nurses, respiratory therapists, laboratory technologists, medical researchers and similarly trained personnel in hospitals, clinics and private physician offices

B. Monitoring:

This clinical study will be monitored by Philips (Sponsor) in compliance with the Code of Federal Regulations (CFR) for clinical research; namely, 21 CFR Parts 50, 54, 56 and 812 and others as applicable. The purpose of such monitoring is to assure that the study remains in compliance with the approved protocol, investigator agreement and regulatory requirements, to verify the completeness, reliability and accuracy of study data and to resolve any issues that arise during the conduction of the study. The Sponsor will conduct monitoring visits periodically as specified by the monitoring plan. Monitoring will be conducted by trained clinical research professionals.

It has been determined that this study does not require a Data Safety Monitoring Board (DSMB).

VI. Assessment of Performance

Device performance will be based on the following recorded Ventilator parameters:

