Categorical data will be presented as frequencies and percentages. Any formal significance testing will be performed at $p < 0.05$.

There are no statistical criteria for terminating the study, and any deviations to the original statistical plan will be noted in the analysis report.

Determination of the Prevalence and Severity of Expiratory Flow Limitation in Chronic Obstructive Pulmonary Disease Patients

Primary Analysis

The primary analysis will calculate the prevalence of EFL, including the 95% Binomial confidence interval (CI).

Secondary Analysis

Correlations between device parameters and efficacy outcomes will be performed using Pearson and Spearman correlation. Percentage of participants exhibiting EFL abolition with Vector therapy will be presented, including the 95% Binomial confidence interval (CI).

Exploratory Analysis

Various exploratory analyses may be performed to help evaluate participant's therapy settings with other baseline data or outcomes, but these analyses are not required for the final report

Participant Disposition

Participant disposition, including the total number of participants enrolled, completed, early terminations and withdrawals, will be presented. A listing will be provided with the reasons for discontinuation.

Safety Analysis

Safety evaluations will be performed by recording clinical adverse events at the time originally reported, and they will be followed at regular intervals until resolution or study completion, whichever comes first. Adverse events will be provided in data listings.

Interim Analysis

An interim analysis may be performed after approximately 50% of the planned study population has completed the study.

X. Direct Access to Source Data / Documents

Only site clinical study staff will know the identity of the participants. All information recorded by the study team and provided for analysis will be given a study ID number.

Privacy rules and requirements according to federal and state governing regulations will be implemented. All the information collected as part of this study will be kept confidential. All information collected for this study will be kept in a secured area or stored in a password protected computer if digital. Except when required by law, participants will not be identified by name, social security number, address, telephone number, or any other direct personal identifier in study records. For records disclosed to Philips participants will be assigned a unique code number.

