This trial will be registered on Clinical Trials.gov. It is the intent that these data may be used for to support regulatory clearance and/or consideration for a submission to peer review publication.

XVI. Risk and Benefit Analysis

A. Potential Risks and Discomforts

This is a minimal risk study. Potential risks are detailed below and will be listed in the ICF and discussed during the consenting process.

We believe that the risks of providing noninvasive ventilation with the Vector NIV device are no greater than the risks encountered with other assisted positive airway pressure (PAP) devices. We believe that no significant risks will be posed to the participants participating in this protocol, as the study is noninvasive and will be conducted in a clinical

Determination of the Prevalence and Severity of Expiratory Flow Limitation in Chronic Obstructive Pulmonary Disease Patients

supervised setting by trained clinical staff. The equipment has been tested to ensure safety. Should the equipment not perform as designed, therapy could increase and / or decrease more than desired. This affect could be uncomfortable.

A trained study staff member will be present monitoring the participant while the device is in use at the clinic. The study staff member will intervene should any problems be identified. One possible intervention could be for the staff to stop the study in the event that participant's oxygen saturation (SpO_2) falls below 88%. The participant can also easily remove their interface device should it become uncomfortable or make breathing difficult. Other potential side effects of PAP therapy may include: ear discomfort, conjunctivitis, skin abrasions due to non-invasive interfaces and gastric distension (aerophagia), all of which are quite uncommon. Thus, we believe that the risks and discomfort are minimal.

COVID-19 is a risk with any in-person activity, but proper mitigation strategies, including COVID-19 screening, disinfection, and other site safety procedures, will be implemented to minimize patient risk.

We believe that the risks and discomforts associated with this study are minimal.

B. Potential Benefits

Although participation in this trial will not result in any direct benefit to the subjects, they will be contributing to generalizable data that will help provide the sponsor and investigator more insight into the prevalence of expiratory flow limitation in the COPD patient population.

C. Compensation for Research-Related Activities

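### The primary prevalence estimate is claimed for a community COPD population, but it will describe only eligible patients at one site, and the planned outputs will not show how selected that group is

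*Combined protocol and SAP*

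**What the plan says.** The target appears in two places. The synopsis (Study Design) and Section III both describe a study "designed to assess the prevalence and severity of expiratory flow limitation in a community COPD population". Section XVI.B goes further and says that participants will contribute "generalizable data that will help provide the sponsor and investigator more insight into the prevalence of expiratory flow limitation in the COPD patient population".

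The group actually studied is defined elsewhere:

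- The synopsis names one university site. No section gives a sampling frame, a recruitment source or a rule for approaching consecutive patients.
- Section IV.A admits people aged 40 to 80 with a COPD diagnosis who can consent. It sets no FEV1 or GOLD limit.
- Section IV.B lists twelve exclusions. Among them are an exacerbation now or in the previous 30 days, "History of bullous emphysema", past pneumothorax, "Participants in respiratory failure" and inability to keep the airway open or clear secretions. Exclusions 7 to 12 repeat the six Vector contraindications in Section V.A.

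Section IX (Primary Analysis) plans the prevalence with a 95% binomial confidence interval. Section IX (Participant Disposition) states: "Participant disposition, including the total number of participants enrolled, completed, early terminations and withdrawals, will be presented". It adds a listing of reasons for discontinuation. It does not ask for the number approached, declined or found ineligible.

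**The concern.** In a prevalence study the denominator defines the result. A percentage among enrolled participants becomes a statement about a wider population only if those participants were sampled from it, or if the reader is told enough about who was left out to judge the difference. This plan provides neither. Several exclusions remove identifiable COPD subgroups, the single site has no stated sampling rule, and the count begins after the selection has largely taken place.

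At stake is the meaning of the primary endpoint. The protocol foresees use of the data for regulatory clearance and publication (Section XV). A figure presented there as community prevalence, with a confidence interval of ordinary width, would look better supported than it is.

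**Working it through.** **The plan's own figure.** Section IX gives about 100 participants and says that no power analysis was done. It states no expected prevalence, precision target or excluded share, so there is no derivation to reproduce.

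**Inputs.** From the documents: n = 100 and a 95% binomial interval. Assumed, because the documents give no values: prevalence p in those enrolled, share e of patients excluded, and prevalence q in those excluded.

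**Step 1: what the interval covers.** Exact (Clopper-Pearson) 95% intervals at n = 100:

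- 20/100: 12.7% to 29.2%
- 30/100: 21.2% to 40.0%
- 40/100: 30.3% to 50.3%
- 50/100: 39.8% to 60.2%

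The half-widths are about 8 to 10 points. They describe random error in the enrolled group. Neither e nor q enters the calculation.

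**Step 2: what selection could do.** Prevalence in enrolled and excluded patients together is

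P = (1 − e)p + eq.

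With q free between 0 and 1, P lies between (1 − e)p and (1 − e)p + e. For p = 30%:

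| Excluded share e | Lowest P (q = 0) | Highest P (q = 1) |
|---|---|---|
| 5% | 28.5% | 33.5% |
| 10% | 27% | 37% |
| 20% | 24% | 44% |
| 30% | 21% | 51% |

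For e = 20%: 0.80 × 0.30 = 0.24, and 0.24 + 0.20 = 0.44. These are extremes. If q were 60%, 30 points above p, the shift would be 0.20 × 0.30 = 6 points upward. If q were 10%, it would be 0.20 × 0.20 = 4 points downward.

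**Step 3: when selection could exceed sampling error.** With u the upper confidence limit, the extreme upward shift e(1 − p) passes u once e > (u − p)/(1 − p). For p = 30% this is (0.400 − 0.300)/0.700 = 14%. The corresponding values are about 12% for p = 20%, 17% for p = 40% and 20% for p = 50%. In the downward direction, with l the lower limit, the condition is e > (p − l)/p, which is about 29% for p = 30%.

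**Step 4: whether the planned outputs supply e.** They do not. A count of patients approached would give the share not enrolled at this site: 125 approached for 100 enrolled gives 1 − 100/125 = 20%, and 150 gives 33%. Disposition that starts at enrolment gives no such number, so a reader cannot tell which side of the Step 3 thresholds the study falls on.

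**The case against.** The strongest reply is that this is mainly wording. The endpoint is already defined as a percentage of participants, the exclusions are reasonable for a session on positive pressure, and the estimate is valid for those enrolled. All of that stands, and it is why the exclusions should not be touched. It does not rescue the community claim, which the synopsis and Section III state as the purpose of the study.

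A second reply also stands in part. Section III has eligibility reviewed after consent, and the plan does not define enrolment. If enrolled means consented, people found ineligible at the visit could appear as early terminations with a reason. It would be too strong to say that exclusions are never reported; what is certainly uncounted is exclusion or refusal before consent. The annual summary to the IRB (Section VII) mentions recruitment but no screening counts, and it is not an analysis output.

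A reader might also infer four things that the documents do not support:

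- *That the estimate errs low.* Section I links resting flow limitation to worsening airflow obstruction. No FEV1 or GOLD limit applies, and no listed criterion excludes oxygen users. (The physical examination item mentions room-air saturation of at least 88%, but it is not in the eligibility list.) Sinusitis, otitis media, epistaxis and hypotension are not presented as markers of COPD severity. Single-site recruitment could act in either direction.
- *That every exclusion was chosen for device safety.* This is well supported for the six that match the contraindications. Bullous emphysema and pneumothorax are not on that list, and no reason is given for them.
- *That removal for bullous emphysema depends on past imaging.* Section III says only that recent scans are collected and "A new CT scan will not be required". It does not say how a history is established.
- *That excluding respiratory failure contradicts the intended use.* Section V.A says "or Respiratory Insufficiency with primary cause being Chronic Obstructive Pulmonary Disease (COPD", which is a different term, and it lists existing respiratory failure as a contraindication directly below.

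**Conclusion.** The concern holds as a mismatch between the stated target and what the design can deliver. The primary estimate will describe patients aged 40 to 80 at one site who met the criteria and agreed to take part. How far that group differs from COPD patients generally cannot be judged from the planned outputs, and the confidence interval does not address the question.

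No size or direction can be assigned. The range of 24% to 44% rests on assumed values (p = 30%, e = 20%) and on letting q take any value; it shows what is left open and is not an estimate of bias. A one-sided figure can be produced only by setting q above p. For example, p = 40% gives 42% with e = 10% and q = 60%, and 55% with e = 30% and q = 90%, but the choice of q fixes the sign in advance. Nor is it right to say that such values lie outside the interval: the exact interval for 40/100, 30.3% to 50.3%, contains most of the range from 42% to 55%. The supportable statement is that the interval does not measure selection at all.

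**What to change.** Leave the exclusion criteria unchanged.

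1. In the synopsis, Section III and the final report, state the target as COPD patients aged 40 to 80 at one centre who meet the study's eligibility criteria. Drop the community claim, and bring Section XVI.B into line.
2. Approach consecutive COPD patients at the site. Keep an anonymous log of those approached, those who declined, and those excluded under each numbered criterion, noting whether exclusion came before or after consent.
3. Extend Section IX (Participant Disposition) to report the log. If a calculation of the form (1 − e)p + eq is shown, run q from 0 to 1 and label it a sensitivity scenario for this site. It is not a bound on community prevalence, because one site's e is not the community's.

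The cost is amended wording, a small logging burden and one additional table, with no added procedures for participants. Approaching consecutive patients is a modest constraint on recruitment, and the headline claim becomes narrower. If enrolment is already under way, the wording can still be corrected in full, and the log can cover the remaining recruitment.
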